3 LIST OF ABBREVIATIONS AND KEY TERMS

3.1 List of abbreviations

AE	Adverse Event
CT	Computed Tomography
EC	Ethics Committee
CRF	Case Report Form
GCP	Good Clinical Practice
IB	Investigators Brochure
MDR	Medical Device Regulation
MPA	Medical Products Agency
MRI	Magnetic Resonance Imaging
PMCF	Post Market Clinical Follow-up
SAE	Serious Adverse Event
SDIEQ	Skin Discoloration Impact Evaluation Questionnaire
SLN	Sentinel Lymph Node
SLNB	Sentinel Lymph Node Biopsy
SOC	Standard of Care
SPC	Summary of Product Characteristics
SPIO	Superparamagnetic nanoparticles of Iron Oxide
Tc99m	Technetium99m
USADE	Unanticipated Serious Adverse Device Effect

3.2 List of key study terms

Terms	Definition of terms
Investigational period	Period of time where major interests of protocol objectives related to defined endpoints are observed, and usually where the test device or comparative device (sometimes without randomization) is given to a subject and continues until the last observation after completing administration of the test device or comparative device.
Treatment number	Number assigned to each subject who has completed all screening assessments successfully at baseline and is willing to be included in the study.
Enrolled subject	Subjects included in the study.
Source data	All information in original records and certified copies of original records of clinical findings, observations, or other activities in a clinical trial necessary for the reconstruction and evaluation of the trial. Source data are contained in source documents (original records or certified copies).
Source documents	Original documents, data, and records including source data.
Subject	An individual who participates in a clinical trial, including screening but not necessarily given study device (enrolment).
Withdrawal	Subject enrolled but did not complete the study for any reason.

4 SYNOPSIS

Title of Study	Sentinel lymph node localisation with an ultra-low dose of superparamagnetic iron oxide nanoparticles in patients with breast cancer
Planned Study Period	4 years, 6 months Enrolment period: 18 months (Q1/2023 – Q3/2024). Follow-up period: 3 years (Q3/2024 – Q3/2027)
Study Objective(s)	The overall aim is to demonstrate that the use of superparamagnetic iron oxide nanoparticles (SPIO) as a tracer in an ultra-low dose (0.1ml) is non-inferior for sentinel lymph node (SLN) detection in patients with breast cancer compared to the dual technique using Tc ^{99m} +/- blue dye, and to evaluate MRI breast artefacts and skin staining over time. Primary objective: To compare SLN detection rates between Magtrace [®] 0.1ml and the dual routine technique with radioactive tracer (Technetium ^{99m} , Tc ⁹⁹) +/- blue dye Secondary objectives: A. To follow MRI breast artefacts for two years B. To follow SPIO and blue dye skin staining for three years
Design and Methodology	A prospective cohort study where all research persons have a SLN biopsy using both SPIO and the dual technique
Number of Subjects Planned	220 patients, based on a non-inferiority design with a 4% margin with each patient being their own control
Endpoints	Primary endpoint: SLN detection rate for Magtrace [®] 0.1ml and for the dual technique (Tc ⁹⁹ +/- blue dye) measured as per cent of patients where a SLN is identified using either the magnetic or the dual technique Secondary endpoints: A. MRI Magtrace [®] artefacts at 3-6, 12 and 24-36 months postoperatively measured as per cent of patients with remaining artefacts evaluated by blinded central review. B. Skin staining due to injected Magtrace [®] and blue dye at 4 weeks, 12, 24 and 36 months measured as per cent of patients with remaining brown or blue skin staining and stain size, evaluated by the investigator and the Skin Discoloration Impact Evaluation Questionnaire (SDIEQ) C. Rate of device-related AEs and SAEs D. Numbers of nodes detected and removed for Magtrace [®] 0.1ml and for the dual technique (Tc ⁹⁹ +/- blue dye) E. Concordance between detected sentinel lymph nodes by Magtrace [®] 0.1ml or by the dual technique (Tc ⁹⁹ +/- blue dye)

Selection Criteria	Inclusion Criteria 1. Age above 18 years 2. Planned for sentinel lymph node biopsy at (or after) breast surgery 3. Signed and dated written informed consent before the start of specific protocol procedures Exclusion Criteria 1. Pregnant or breast-feeding 2. Iron overload disease 3. Known hypersensitivity to iron, dextran compounds or blue dye. 4. Inability to understand given information and give informed consent or undergo study procedures
Discontinuation Criteria	Subjects must be discontinued from the study for the following reasons: 1. Inappropriate enrolment (violation of Inclusion / Exclusion Criteria) 2. Withdrawal of consent 3. Due to safety reasons judged by the Investigator

5 INTRODUCTION

5.1 Background

Breast cancer is the most frequent cancer in women with approximately 10,000 new patients in Sweden yearly (The National Board of Health and Welfare of Sweden, www.socialstyrelsen.se). The sentinel lymph node (SLN) is the first lymph node that receives lymphatic drainage from the primary tumour site. Sentinel lymph node biopsy (SLNB) is an established technique for tumour staging in breast cancer patients [1]. The SLN is usually detected by the dual technique of injecting a radioactive isotope (Technetium^{99m}, Tc⁹⁹) and a blue dye (Patent bleu[®]) in the breast. The SLN is identified by a handheld gamma-probe and the dye stains the SLN with a blue colour which makes it easy to visualize during surgery.

A new SLN tracer containing superparamagnetic nanoparticles of iron oxide (SPIO/Magtrace[®]) has shown similar detection rates as for the dual technique [2-4]. Magtrace has been injected interstitially (intra/peri-tumourally or subcutaneously behind the areola) before surgery and the SLNs are detected during surgery with a handheld probe (SentiMag[®]) that measures the strength of the magnetic field created by the magnetic tracer.

After the use of SPIO/Magtrace[®] in breast cancer there is a risk of magnetic resonance imaging (MRI) artefacts after breast conserving surgery, as well as a risk for long-lasting skin staining after the injection. A feasibility study in melanoma, the MAGMEN study, have reported promising results using a ultra-low dose of 0.1 mL Magtrace[®], that was injected intradermally [5]. In a feasibility study including 30 patients with breast cancer, we have shown that the SLN was detected in all 30 patients with a similar intradermal injection of 0.1ml SPIO/Magtrace[®] (results not yet published). This ultra-low dose of Magtrace[®] would potentially reduce the drawbacks of SPIO related MRI artefacts and skin staining.

6 STUDY OBJECTIVES AND DESIGN

6.1 Study objectives

The overall aim is to evaluate the use of superparamagnetic iron oxide nanoparticles (SPIO) as a tracer in an ultra-low dose (0.1ml) is non-inferior for sentinel lymph node (SLN) detection in patients with breast cancer compared to the dual technique using Tc^{99m} and blue dye, and to evaluate MRI breast artefacts and skin staining over time.

Primary objective:

SLN detection rate for Magtrace® 0.1ml and for the dual technique (Tc⁹⁹ +/- blue dye) measured as per cent of patients where a SLN is identified using either the magnetic or the dual technique

Secondary objectives:

- A. To follow MRI breast artefacts for two to three years
- B. To follow SPIO and blue dye skin staining for three years

6.2 Study endpoints

Primary endpoint:

SLN detection rate for Magtrace® 0.1ml and for the dual technique (Tc⁹⁹ +/- blue dye) measured as per cent of patients where a SLN is identified using either the magnetic or the dual technique

Secondary endpoints:

- A. MRI Magtrace® artefacts at 3-6, 12 and 24-36 months postoperatively measured as per cent of patients with remaining artefacts evaluated by blinded central review.
- B. Skin staining due to injected Magtrace® and blue dye at 4 weeks, 12, 24 and 36 months measured as per cent of patients with remaining brown or blue skin staining and stain size, evaluated by the investigator and the Skin Discoloration Impact Evaluation Questionnaire (SDIEQ)[8]
- C. Rate of device-related AEs and SAEs
- D. Numbers of nodes detected and removed for Magtrace® 0.1ml and for the dual technique (Tc⁹⁹ +/- blue dye)
- E. Concordance between detected sentinel lymph nodes by Magtrace® 0.1ml or by for the dual technique (Tc⁹⁹ +/- blue dye)

6.3 Risk-benefit evaluation

The magnetic technique is already approved for SLN diagnostics in breast cancer. The results are comparable to the clinically routine use of Tc⁹⁹ and blue dye. The risk of using a lower dose of Magtrace® is that the SLN is not detected. An ultra-low dose of Magtrace® for identifying the SLN has been explored in a feasibility study with 30 patients and in all patients the SLN was detected. Also, in this study Tc⁹⁹ +/- blue dye will be used in parallel as a comparison and back up minimising the risk of an unsuccessful SLNB.

For the study participants the study will result in an extra injection that can be painful but only for a short time. Skin staining from the Magtrace® can occur but as Magtrace® is currently used as a routine tracer in Sweden in a ten times higher dose, the benefit of testing a lower dose is greater than the risk of a small skin staining. The skin staining is also one of the outcomes that will be followed.

In a subgroup of included persons, two to three breast MRIs will be performed after 3-6, 12 and 24-36 months. MRI is painless and does not cause ionising radiation, but some people find the tight space discomfoting. This part of the study is optional and up to the research person's. The magnetic field could affect metal objects which are inside the body. Therefore, persons with surgical implants (e.g., insulin pump, or pacemaker) will be excluded from this part of the study.

Participating in the study also takes extra time and personal data is to be handled. The risk of breaking their integrity is considered as small in this study. All patients are given information about both the benefits and risks of the research. They can then voluntarily decide whether they want to participate or not, and they can withdraw their consent at any time.

In summary, the risk of being included in this trial is assessed to be low, and we have not identified any ethical problem in a broader perspective. The study participants contribute to advancing research on SLN and staging technology, which may be useful for other patients in the future.

6.4 Study design and procedures

6.4.1 Overall study design

This is a prospective cohort study comparing an ultra-low dose of 0.1 mL Magtrace® with the dual technique with Tc99 +/- blue dye for SLN detection with a non-inferiority design. There is no randomisation but instead every person is their own control, i.e., the patient will have the SLN identified with both tracer methods. This study design has already been used in several international studies and 220 persons will be included at four study sites, during 18 months.

Skin staining will be documented at the first follow up at four weeks with measurements of size of staining performed and documented with a photograph if staining is present for either SPIO or blue dye. Skin staining will be followed for three years after surgery. Those with a remaining skin staining at the routine 12 months follow up will be followed by telephone interview or physical visit at 24 and 36 months.

Furthermore, up to 50 persons will be included for secondary objective A, for evaluation of MRI artefacts in the operated breast at 3-6, 12, and 24 months. All MRI and corresponding mammograms will be evaluated centrally regarding artefacts and breast density.

6.4.2 Procedures

An intradermal dose of 0.1ml Magtrace® will be injected up to 30 days before surgery. The injection should be in the skin over the tumour, or at the border of the areola. A pre-operative photo of the breast will be taken, including any staining.

Before surgery Tc⁹⁹ is injected in the breast as per routine practice. Blue dye is optional and if used, it is injected after induction of anaesthesia. During surgery, SLNs are first identified with the SentiMag[®]-probe. The dual technique, with the gamma probe +/- blue dye will be used afterwards, confirming each removed SLN and for detection of additional SLNs. For each tracer, the following parameters will be recorded in the CRF: transcutaneous magnetic and radioactive signals in breast and axilla, number of nodes, the colour of the nodes, signals in vivo and ex vivo for each SLN, residual transcutaneous signals at the end of surgery in breast and axilla. A lymph node is considered a SLN if it contains more than a 10% activity compared to the maximum activity of the highest scoring lymph node (first SLN) with either tracer. Each SLN will be sent separately for routine histopathology with the specific question concerning microscopically detected SPIO. For all patients, the pathologists are requested to report the lymph node status separately.

At the first post-operative visit (approximately 4 weeks after surgery) blue and brown skin staining will be recorded by photography including a centimetre scale, and any residual magnetic signal will be measured in the breast. In those patients with a remaining skin staining this procedure will be repeated at 12 months, and after 24 and 36 months by telephone interview without a photo or a physical visit. Patients will be asked about how they experience the staining according to a 5-point Likert scale (Skin Discoloration Impact Evaluation Questionnaire (SDIEQ))[8].

In up to 50 patients, a postoperative routine MRI of the breast, with contrast medium will be performed at 3-6, 12 and 24-36 months after surgery to evaluate the presence of SPIO artefacts. MRI artifacts and mammographic density will be recorded in a separate CRF by the radiologists and then transferred to our CRF.

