11 STATISTICS

11.1 Statistical methods

We estimate the SLN detection rate to be about 98% for both Magtrace[®] and the dual technique based on our earlier feasibility study where all patients had a successful SLN-biopsy with 0.1ml Magtrace[®] intracutanously. The detection rate for the dual technique is estimated based on our earlier studies, i.e., Nordic Trial, Monos and SentiDose trials. We set an acceptable difference in SLN-detection rate to 4%. If there is truly no difference between the dual technique and the experimental 0.1ml Magtrace[®], then 386 patients would be

required in a randomised study to be 80% sure that the upper limit of a one sided 97.5% confidence interval will exclude a difference in favour of the dual technique of more than 4%. As every patient is their own control the sample size required is 193. Allowing for a dropout rate of approximately 10%, 220 patients will be recruited.

For the second endpoint skin staining, a subgroup of patients will be included in the analyses. Regarding skin staining, only patients undergoing breast conserving surgery will be included. As breast conserving surgery is done in approximately 85% of all patients, this cohort will include approximately 187 patients.

For the second endpoint, MRI artefacts, 50 of the 187 patients undergoing breast conserving surgery will be asked separately if they accept doing an MRI at 3-6, 12 and 24-36 months postoperatively. These patients will only be included in Gothenburg and Uppsala. They are recruited consecutively, and inclusion stops when 50 have accepted participation.

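### Magtrace may be injected in skin that the operation removes, and the staining endpoint as written counts an excised stain the same as one that faded

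*Protocol*

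**What the plan says.** Protocol section 6.4.2 allows two injection sites and gives no rule for choosing between them: "The injection should be in the skin over the tumour, or at the border of the areola".

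Secondary endpoint B (section 6.2) is "measured as per cent of patients with remaining brown or blue skin staining and stain size", at 4 weeks and at 12, 24 and 36 months, together with a patient questionnaire. Section 11.1 defines who is analysed: "Regarding skin staining, only patients undergoing breast conserving surgery will be included". It then sizes the group: "As breast conserving surgery is done in approximately 85% of all patients, this cohort will include approximately 187 patients".

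The first scoring for the endpoint comes after the operation: "At the first post-operative visit (approximately 4 weeks after surgery) blue and brown skin staining will be recorded by photography including a centimetre scale". Footnote a to the flow chart in section 6.4.3 stops follow-up once the stain has disappeared, without asking why. The footnote is attached to both photography and residual magnetic activity.

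On recording, section 6.4.2 says "For each tracer, the following parameters will be recorded in the CRF". The list covers magnetic and radioactive signals through the skin of breast and axilla, then "number of nodes, the colour of the nodes, signals in vivo and ex vivo for each SLN", and finally the signals left in breast and axilla at the end of surgery. It names neither the injection site used nor whether the injected skin was removed. The section also plans a photograph before surgery: "A pre-operative photo of the breast will be taken, including any staining".

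**The concern.** Restricting the analysis to breast-conserving surgery removes mastectomy patients, whose staining result would say little about the tracer. It does not deal with a breast-conserving operation, or a re-excision, that takes the skin over the tumour. If Magtrace was injected there, the stain leaves with the specimen. At 4 weeks that patient has no stain, enters the percentage as unstained, and is not followed further.

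This matters because section 5.1 justifies the 0.1 ml dose partly by the hope of less staining and fewer MRI artefacts. A reader will take endpoint B as evidence on how often and how long this dose stains. For that use the error runs one way, in favour of the low dose. The result would also depend on how often each of the four study sites injects over the tumour, so it could not be applied directly to a clinic that uses the areolar border.

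**Working it through.** **Inputs from the protocol (section 11.1).** 220 patients recruited; about 85% with breast-conserving surgery.

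**Inputs not in the protocol, assumed here.** The share q of the staining cohort whose injected skin is excised: 0 to 50%. The true staining rate if no skin were excised: 20%, 40% or 60%. No section says how often skin over the tumour is removed, so q = 0 belongs in the range.

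**Step 1. The plan's own figure.** 0.85 × 220 = 187. It reproduces exactly and is not in dispute.

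**Step 2. What the endpoint counts.** Assume that excision is unrelated to the tendency to stain and that an excised patient counts as unstained. Then

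observed rate = (1 − q) × true rate

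| True rate | q = 0 | q = 10% | q = 20% | q = 30% | q = 50% |
|---|---|---|---|---|---|
| 20% | 20% | 18% | 16% | 14% | 10% |
| 40% | 40% | 36% | 32% | 28% | 20% |
| 60% | 60% | 54% | 48% | 42% | 30% |

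**Step 3. Against sampling error.** The standard error is √(p(1 − p)/187). For p = 20% it is √(0.16/187) = 2.9 points; for 40% or 60% it is √(0.24/187) = 3.6 points. At q = 10% the shifts are 2, 4 and 6 points, so the shift exceeds one standard error at 40% and 60% but not at 20%. At q = 20% the shifts are 4, 8 and 12 points and exceed it in all three cases.

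**Step 4. Dependence on injection site.** Let a be the share injected over the tumour, and let e₁ and e₂ be the excision shares for the tumour and areolar sites. Then q = a·e₁ + (1 − a)·e₂. If e₁ differs from e₂, two centres with the same true staining rate report different rates whenever a differs.

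**Step 5. What is not distorted.** Skin removed at the first operation is already missing at 4 weeks. The ratio of a later rate to the 4-week rate is (1 − q)·s₁₂ / ((1 − q)·s₄) = s₁₂/s₄, where s₄ and s₁₂ are the true rates at 4 weeks and 12 months. Fading among patients stained at 4 weeks is therefore unaffected, unless a later re-excision takes the stain.

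**The case against.** Five points can be made for the plan.

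- **The information is not wholly lost.** Breast magnetic signal is recorded before removal of the nodes, at the end of surgery and at about 4 weeks, and a marked fall suggests that the deposit was removed. A pre-operative photograph set beside the 4-week one could show whether the stained skin is still there. Medical records are source documents. This stands, so a reader who infers that the excised share can never be recovered goes too far. But the evidence is indirect: a low signal does not name the injection site or prove that skin was removed, and no section links it to endpoint B. The photograph is also uncertain. The text of section 6.4.2 implies that it is taken after injection, while the flow chart ticks it at screening, in the column before Magtrace is given.
- **The section 6.4.2 list is not a full CRF.** It also omits stain size and type of surgery, which the analysis needs. This is correct. The claim is only that no listed item names the injection site or skin removal.
- **The analysis plan may deal with it.** It can set denominators and sensitivity analyses, but it needs the two variables to have been collected.
- **A patient without a stain is unstained, whatever the cause.** This stands for the cosmetic outcome, and the questionnaire fits that reading. The planned rate is therefore not wrong in itself. It is wrong only when read as persistence of the tracer.
- **The magnitude has no anchor.** This is true. Both the true rate and q are assumed, and at q = 0 there is no bias.

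**Conclusion.** The point holds for staining. With two permitted injection sites, a population defined only by breast conservation, a first scoring after surgery and a stopping rule that ignores the cause, the endpoint as written cannot separate excision from fading. Excision can only lower the observed rate relative to persistence in retained skin. Its size is unknown: at an assumed true rate of 40% the loss is 0, 4, 12 or 20 points for q = 0, 10%, 30% or 50%, on the assumption that excision is unrelated to staining tendency.

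A reader might infer that the MRI artefact rate is biased by the same factor. The documents do not support that. They do not say how much of an artefact comes from the injected skin, and nothing here quantifies it. For MRI the point justifies a description by site status and no more.

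This is a secondary, descriptive endpoint. The detection-rate analysis and its sample size are not touched. The change is worth making because the mechanism is clear and the remedy is nearly free.

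**What to change.** Add two CRF items: the Magtrace injection site (over the tumour or at the areolar border), and whether the injected skin was removed at the operation or at a re-operation. This is a matter of recording only; it does not ask for a different injection site or a different operation.

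Keep the planned percentage in all breast-conserving patients and label it as the cosmetic outcome. Beside it, report the staining rate among patients whose injected skin was retained, described by injection site, with excised cases as a separate category. For the MRI group of up to 50 patients, only describe artefact presence by whether the site was retained, since further splitting would leave very small groups. Reconcile the timing of the pre-operative photograph between sections 6.4.2 and 6.4.3.

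The cost is two CRF fields and a smaller denominator for the added rate, 187 × (1 − q). At q = 10%, 30% and 50% that is about 168, 131 and 94 patients. At a rate of 40% the standard error √(0.24/n) rises from 3.6 points to about 3.8, 4.3 and 5.1.

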6.4.3 Flow-chart/time and events schedule

	Screening	Day		Week	Months			
		-30 to 0	0	4 +/-2	3-6 +/-1	12	24	36
Eligibility assessments								
Informed Consent	X							
Inclusion/Exclusion Criteria	X							
Clinical Procedures								
Photography ^a	X			X		X	X*	X*
Administration of Magtrace ^b		X						
Administration of Tc ⁹⁹ +/- blue dye			X					
Surgery			X					
Residual magnetic activity ^a			X	X		X	X	X
MRI breast*					X	X	X**	X**

*Optional, **One MRI between 24 and 36 months, ^aFollow up is ended when the stain is gone. ^bMagtrace injection 0-30 days before surgery.

